## Aim 2: Assess PEEPS implementation factors

### 2a. Evaluate barriers and facilitators to PEEPS success.

**Overview:** Given the urgent need for effective endometriosis-related pain treatments, developing an intervention that can be expeditiously translated into clinical practice is just as important as developing an effective intervention. Thus, I will use the *Characteristics of Individuals* and *Process* domains from the CFIR framework to understand the implementation barriers and facilitators of PEEPS. In D&I science, "context" describes the circumstances and unique factors that surround intervention implementation efforts (in this case PEEPS), including barriers and facilitators to intervention success. A thorough understanding of context can help guide intervention adaptations and development of strategies to support intervention implementation.

**Consolidated Framework for Implementation Research (CFIR):** CFIR is a comprehensive implementation framework that will provide a structured way to approach the multi-level implementation of PEEPS. Guided by constructs in the *Intervention Characteristics* (e.g. relative advantage, complexity, design quality) and *Process* domains (Planning, Executing, Reflecting and Evaluating), I will assess PEEPS taking into consideration that patients and clinicians are active participants, inherently evaluating and developing feelings about the intervention.

### 2b. Assess implementation outcomes of PEEPS.

**Overview:** Implementation outcomes are indicators of implementation success and can be used to distinguish implementation effectiveness from treatment effectiveness, a key step necessary to transition from a research protocol to community health. If an intervention is not implemented well, treatment will not be effective. Given PEEPS' inter-disciplinary group care approach, it is important to understand implementation outcomes at both the patient and clinician levels.

**Implementation Outcomes Framework (IOF):** Proctor et al.'s *Implementation Outcomes Framework* provides a practical structure to measure and determine implementation effectiveness. The three early implementation outcomes of *acceptability*, *appropriateness*, and *feasibility* will guide assessment of PEEPS implementation in this pilot RCT (**Table 2**). These early outcomes are markers of implementability of a future intervention. Details of *acceptability* and *appropriateness* are described in Table 2. As part of the *Feasibility* evaluation, we will analyze recruitment data, patient demographics, referral locations, referring provider characteristics, reasons for declining participation, and percentage of participants who complete each PEEPS session. This will allow us to determine the recruitment volume needed at each site for the future multi-site trial.

**2.1. Data collection:** I will administer valid and reliable surveys to PEEPS participants and facilitators weekly during session "Closing" time, and a summative survey at intervention completion (**Table 2**). These surveys contain Likert scale, dichotomous, and open-ended items. Participants will be notified that this feedback will be reviewed at study completion, and that pressing concerns should be addressed with one of the facilitators.

**Table 2. Data Collection for implementation barriers and facilitators (i.e. context) and implementation outcomes (Aims 2a and 2b)**

Factor	Definition	Level	Sample Type and Analysis	Aim and Framework
Intervention Characteristics				Aim 2a CFIR
Relative advantage	Advantage/disadvantage relative to existing treatments	Patient/Clinician	· Validated, Quantitative 	
Complexity	Perceived difficulty of intervention and disruptiveness to daily life	Patient/Clinician	· Validated, Quantitative  · Future PEEPS timing (summative)	
Design quality	Perceived excellence of intervention, format, and content	Patient/Clinician	· Validated, Quantitative, Qualitative 	
Process				Aim 2a CFIR
Planning	Quality of intervention delivery method	Patient/Clinician	· Quantitative, Likert scale · Suggestions for improvement, Qualitative	

Program execution	Carrying out intervention according to plan	Patient/ Clinician	· Validated, Quantitative, Qualitative 	
Reflecting & Evaluating	Feedback on experience with intervention	Patient	· Most helpful part, Qualitative · Least helpful part, Qualitative	
Acceptability	Stakeholder perception if PEEPS is agreeable/ satisfactory	Patient/ Clinician	· Satisfaction with intervention- Validated, Quantitative, Qualitative  · Likelihood of recommending to peer Quantitative, Likert scale	Aim 2b IOF
Appropriateness	Perceived fit, relevance, and compatibility of PEEPS Perceived cultural appropriateness of PEEPS	Patient  Clinician	· Appropriateness of material, Validated, Quantitative  · Session flow, Validated, Qualitative  · Participant engagement, Qualitative · Group dynamics, Qualitative	Aim2b IOF
Feasibility	Extent to which PEEPS can be successfully carried out	Patient	· Administrative data on recruitment, enrollment, retention, Quantitative	Aim 2b IOF

CFIR, Consolidated Framework for Implementation Research; IOF, Proctor's Implementation Outcomes Framework.

**2.2. Outcome measures:** After completion of all PEEPS sessions, we will use a mixed methods approach that includes descriptive statistics and content analysis. Categorical survey outcome data will be analyzed using chi-square or Fisher's exact tests as appropriate. Ordinal survey outcome data will be analyzed using the Mann-Whitney U test. A p-value of 0.05 will be used to assess significance. Qualitative data from open-ended survey responses will be entered and analyzed in NVivo 12 software. Qualitative data will be analyzed for *a priori* and emerging themes. We will examine satisfaction using sentiment analysis of major and sub-themes. We will then triangulate the quantitative and qualitative data to gain insight on the constructs measured in Table 2. These findings will be used to optimize PEEPS in preparation for the definitive multi-center effectiveness RCT.

## PROTECTION OF HUMAN SUBJECTS

### 1. Risk to Human Subjects

**1a. Human Subjects Involvement, Characteristics, and Design.** This study is a pilot randomized controlled trial of people with endometriosis-related chronic pelvic pain. Patients meeting inclusion criteria will be enrolled from the outpatient OB/GYN clinic setting. Patients will be recruited for sequential 8-week PEEPS cohorts with a goal of 6-10 subjects participating in each cohort. Enrolled patients will be randomized to PEEPS plus usual care versus usual care alone. Recruitment and randomization will continue until 30 participants in the PEEPS arm attend at least one PEEPS session. Randomization will occur in REDCap with the assistance of the study statistician.

**1b. Study Procedures, Materials, and Potential Risks.** This study will involve collection of data from two key components.

1) Clinical data collection: Relevant clinical and demographic data will be abstracted from medical records including medical and psychosocial history, and prior and current treatments for endometriosis (medications, physical therapy, surgery, counselling, alternative therapies). This data will be abstracted from the patients medical records. For all subjects, these data will be stored in a secure, password-protected REDCap database anonymized with study identifier only. No private identifiable information will be collected.

2) Survey data collection: Subjects in both arms will complete surveys at baseline (defined as the month leading up to the first PEEPS session for their cohort), PEEPS completion, and 6- and 12-months after completion. The validated patient-reported outcomes measures will assess pain severity, physical function, history of sexual trauma, mood symptoms, other quality of life measures, and experiences of discrimination in healthcare. This survey data will also be collected and stored in the password-protected REDCap database.

The proposed study involves potentially rare risks to the subjects, including loss of confidential health information, musculoskeletal injury to patients while participating in the yoga and physical therapy components, emotional distress in completing validated surveys on mental health, and excessive demands on patients. Patients with endometriosis and chronic pelvic pain have intermittent pain exacerbations, sometimes due to common triggers such as menses, ovulation, or intercourse, but many exacerbations are unpredictable and

sporadic. It is possible that participating in PEEPS might a pain trigger for some participants. Protections against anticipated risks are outlined below under “Adequacy of Protection Against Risk.”

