To adapt *Centering Chronic Pelvic Pain* to be specific to patients with endometriosis, I assembled an interdisciplinary team of collaborators: [name], an expert in chronic pain clinical psychology; [name] and [name], an expert in women's health physical therapy; and [name], an expert in yoga, physical therapy, and group care. Together we developed Peer-Empowered Endometriosis Pain Support (PEEPS), which integrates three evidence-based approaches. 1) Physical therapy improves the pelvic floor and musculoskeletal components of pain, 2) Mindfulness interventions improve global impression of change, overall quality of life, and anxiety and depression, 3) Yoga reduces pain and improves emotional well-being and sexual function. Given that PEEPS combines an interdisciplinary team approach, an integrative setting, and group care into one program incorporating evidence-based components, it is likely to be an effective strategy to treat patients with endometriosis-associated pain. However, since these evidence-based interventions have not been bundled and delivered in this way before, effectiveness of this approach must be evaluated. Given the urgent need for translation of effective treatments into practice, I will take an implementation science approach to understand the implementation outcomes of PEEPS and the implementation context (or barriers and facilitators) of PEEPS.

Here, I propose to conduct a pilot clinical trial in which 40 patients with endometriosis and chronic pelvic pain attend PEEPS in addition to usual care. Within this trial, I will test the **central hypothesis** that PEEPS will lead to decreased endometriosis-related pain interference, improved quality of life, and decreased pain catastrophizing by pursuing the following **specific aims**:

**Aim 1: Measure preliminary effectiveness of PEEPS.** I will use validated patient-reported outcomes measures to assess preliminary effects on pain interference and quality of life. I **hypothesize** that patients in PEEPS will show decrease in pain interference in daily activities at program completion and 6-months post-completion than at baseline. With 40 patients attending PEEPS this pilot trial will assess both preliminary effectiveness as well as implementability of PEEPS.

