## APPROACH

### Aim 1: Measure preliminary effectiveness of PEEPS

**1.1. Patient population and recruitment:** This pilot clinical trial will be conducted through the Department of OB/GYN at WUSTL. Forty patients will be recruited to participate in an 8-week curriculum of PEEPS. To equitably recruit a diverse group of participants, including those historically excluded from research, we will recruit from three sites: WUSTL Minimally Invasive Gynecologic Surgery (MIGS) (a sub-specialty referral practice), WUSTL General OB/GYN clinics, and Affinia Healthcare (a Federally Qualified Health Center). If a patient is eligible and elects to participate, written informed consent will be obtained in person while at a clinic visit, or via email or fax when the study is discussed by phone.

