#### Inclusion and exclusion criteria:

Inclusion criteria	Exclusion criteria

• Age 18-48 years

• Operative confirmation of endometriosis

• Chronic pelvic pain (defined as pain perceived to originate from the pelvis, lasting <math>\geq 6</math> months)

• No plan to have surgery in next 12 weeks

• Be able to attend eight 2-hour weekly sessions on the WUSTL campus

	

• Non-English speaking

• Currently pregnant

• Severe physical impairment

• History of hip, back, or spine surgery

• Opioid use <math>\geq 5</math> days in the past 3 months, other than for the 6-week post-operative period

• Current or history of psychiatric disorder with psychosis

**1.2. Data collection:** Participants will be recruited for sequential 8-week PEEPS cohorts with a goal of 6-10 subjects in each cohort. At baseline, we will collect data on medical and psychosocial history, and prior and current treatments for endometriosis (medications, physical therapy, surgery, counselling, alternative therapies). Participants will complete baseline questionnaires prior to the first session of PEEPS, within one month of PEEPS completion, and at 6-months post-completion. Surveys will be administered in Research Electronic Database Capture (REDCap), and the following measures will be administered:

- PROMIS pain interference SF 8a: validated, 8 questions, assesses pain interference in daily activities
- PROMIS pain intensity: validated, 3 questions, measures pain on a 1-5 scale over the past 7 days
- Endometriosis Health Profile-30: validated, 30 questions, endometriosis-related quality of life measure
- PROMIS Physical Function SF10a: validated, 10 questions, measures physical activities of daily living
- PROMIS Anxiety SF7a: validated, 7 questions related to anxiety in past 7 days
- PROMIS Depression SF8b: validated, 8 questions related to depression in past 7 days
- Female Sexual Function Index: validated, 19 questions
- Pain Catastrophizing Scale: validated, 13 questions
- Patient Global Impression of Change: validated, 1 question, on a 0-10 continuous scale

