- Modified Everyday Discrimination Scale: validated, 9 questions, with 10 follow up questions if discrimination ongoing to assess experiences of healthcare discrimination
- Personal goals: I will ask participants to identify three personal goals related to quality of life that they hope to achieve by participating in PEEPS, such as “Be able to go on a hike without pain limiting my activity”.

Patients will receive a unique link to their questionnaires at each of the three time points. Participants who do not respond will be sent three reminder messages and receive up to two completed phone call reminders. The research team will be responsible for day-to-day study supervision and data management. The study statistician will perform monthly data quality control analysis for missing values and data discrepancy and create monthly data reports on screening and recruitment. Data security will be maintained by using dedicated password-protected, encrypted computers with multiple backups.

**1.3. Analysis plan:** This is a pilot observational trial of a novel intervention where preliminary effect size is unknown. Recommendations for pilot clinical trials suggest using 12-70 subjects. Enrolling 40 subjects will reduce imprecision around the standard deviation estimate and allow for sufficient participants in PEEPS to assess implementation factors. We hypothesize that patients engaging in PEEPS will experience less pain interference after completing PEEPS than at baseline. Descriptive statistics and two-sample t-test will be performed for numeric variables with normal distribution, Wilcoxon Rank Sum test if not normal distribution. Frequency analysis and Fisher exact or Chi-square test for categorical variables will be performed as appropriate. Longitudinal analysis on primary outcomes and secondary outcomes using paired t-test

comparing each time point (completion and 6-months) to baseline. Mixed effects model will be used for fixed effect of PEEPS compared to baseline over time with random effect of intercepts. For categorical outcomes, we will calculate relative risk and 95% confidence intervals.

**1.4. Feasibility of recruitment and retention:** Patients will receive \$25 for completion of the baseline questionnaire and \$50 for each of the two other time points (completion and 6-months). Patients who complete all portions of the study will receive a total of \$125.

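### The protocol describes two incompatible designs: a single group of 40 patients who all receive PEEPS, and a randomised comparison of PEEPS with usual care alone

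*Combined protocol and SAP*

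**What the plan says.** All of the text below is in the Combined protocol and SAP, and all of it is current.

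**Single-group description.** The Protocol Synopsis proposes "a pilot clinical trial in which 40 patients with endometriosis and chronic pelvic pain attend PEEPS in addition to usual care". Its Aim 1 hypothesis is "that patients in PEEPS will show decrease in pain interference in daily activities at program completion and 6-months post-completion than at baseline", and it adds: "With 40 patients attending PEEPS this pilot trial will assess both preliminary effectiveness as well as implementability of PEEPS". Section 1.1 repeats the number: "Forty patients will be recruited to participate in an 8-week curriculum of PEEPS". Section 1.2 places the follow-up questionnaires "within one month of PEEPS completion, and at 6-months post-completion", and says: "Patients will receive a unique link to their questionnaires at each of the three time points". Section 1.3 labels the study: "This is a pilot observational trial of a novel intervention where preliminary effect size is unknown". Its longitudinal analyses are paired t-tests of completion and of 6 months against baseline, and a random-intercept mixed model that also takes baseline as the reference. Section 1.4 pays $25 for the baseline questionnaire and $50 for each of completion and 6 months, $125 in total.

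**Randomised description.** Protection of Human Subjects, section 1a, calls the study a randomised controlled pilot and says: "Enrolled patients will be randomized to PEEPS plus usual care versus usual care alone". Allocation is done in REDCap with the statistician's help. Recruitment stops once 30 patients in the PEEPS arm have attended at least one session. Section 1b surveys both arms at baseline, completion, 6 months and 12 months. Aim 2, section 2b, also refers to the present study as a pilot RCT, without further detail.

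**The concern.** The design determines what Aim 1 estimates. In a single group, the result is a change from baseline with no control. It mixes any effect of PEEPS with regression to the mean, the natural fluctuation of pain, and whatever usual care contributes. In a randomised comparison, the result is a difference from usual care alone.

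The same choice decides whether a patient who consents may be allocated to no PEEPS at all, when recruitment stops, and whether a 12-month survey is run. The document answers each of these questions twice, and differently. The human-subjects section is where allocation and procedures are described for the protection of participants, so a wrong description there matters even in a pilot.

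**Working it through.** This is a comparison of texts. The only arithmetic concerns payments and what the 30-attender rule would imply.

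**Side by side**

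| Item | Synopsis and sections 1.1 to 1.4 | Protection of Human Subjects, 1a and 1b |
|---|---|---|
| Label | Observational pilot (1.3) | Randomised controlled pilot (1a; label also in Aim 2, 2b) |
| Who receives PEEPS | All 40 (synopsis, 1.1) | Only those allocated to it |
| Recruitment ends | At 40 | At 30 PEEPS-arm attenders; no total N, no ratio |
| Surveys | Three: baseline, completion, 6 months | Four, in both arms: the same three plus 12 months |
| Longitudinal contrast | Each time point against baseline (1.3) | None given |

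The cohort size of 6 to 10 appears in both descriptions, so it does not separate them.

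**Step 1. Can both be followed?** In the synopsis and section 1.1, the number of enrolled patients not sent to PEEPS is 0. In section 1a it must be above 0, because one arm gets usual care alone. No ratio makes these equal, so the texts conflict before any calculation.

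**Step 2. The plan's own figures.** The 40 is supported in section 1.3 by a cited pilot range of 12 to 70 and by precision of the standard deviation. No effect size, SD, power or target precision is given, so it cannot be re-derived. The payment total does reproduce: 25 + 50 + 50 = $125. That uses up the total on three surveys, so nothing is stated for a fourth.

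**Step 3. What the 30-attender rule implies (illustration only).** With r PEEPS patients per control and full attendance, total N = 30 × (1 + 1/r):
- 1:1 gives 30 + 30 = 60.
- 2:1 gives 30 + 15 = 45.
- 3:1 gives 30 + 10 = 40.

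If 80% of the PEEPS arm attended, that arm would need 30/0.8 = 37.5, so 38 patients. The total would be 38 + 38 = 76 at 1:1, or 38 + 19 = 57 at 2:1. The ratios and attendance rates are assumptions. They show that total N is left open under this rule.

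**Step 4. Does the analysis plan serve the randomised version?** The paired t-tests and the mixed model both refer to baseline, and no arm or arm-by-time term is described. The two-sample tests and relative risks in section 1.3 name no groups. A randomised trial would therefore have no defined between-arm longitudinal comparison. The 12-month survey appears in no analysis.

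**The case against.** The best defence is that the randomised wording is left over from another design. The hypothesis, N, survey schedule, payments, longitudinal analysis and the label in section 1.3 all fit a single group, and the synopsis carries a version date. The randomised text is confined to Protection of Human Subjects and one label in Aim 2. That is a fair reading of the weight of the text. But section 1a is more than a stray label: it gives an allocation mechanism, a stopping rule, two arms and a longer follow-up. It is not in an amendment log, and nothing says it has been replaced. The definitive multi-centre RCT mentioned in section 2.2 is a future study and does not explain it. A reader may think the single-group design is the intended one; the documents do not say so.

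It can also be said that the two-sample tests in section 1.3 are the between-arm comparison. They might be, but no groups or time points are named. The missing group names need attention under either design and are not proof of the conflict.

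Three stronger readings are tempting and should not be drawn:
- **That 40 patients cannot yield 30 PEEPS attenders.** At an assumed 1:1 split, 40 gives 20 in PEEPS, 10 short. At 3:1 with full attendance it gives exactly 30. No ratio is stated, so the shortfall is not established, and the conflict does not need it.
- **That the payment sections disagree.** Section 1.4 already says which surveys are paid, and the $25 to $50 gift cards under Burden to Patients match those amounts. The only gap is the 12-month survey.
- **That one design is statistically better because it is more precise.** A before-after change and a between-arm difference are different estimands, so their precision cannot be ranked as if they answered one question. Neither design is criticised here on its merits.

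**Conclusion.** The point holds as an internal inconsistency that must be fixed. The rules on allocation, on ending recruitment and on the survey schedule cannot all be followed. In size: all 40 patients in PEEPS against an unstated fraction; a fixed N of 40 against a total that could be 40, 45 or 60 at the three ratios illustrated with full attendance, and more with incomplete attendance; three surveys against four.

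The contradiction itself rests on no assumption. Only the illustrative totals do, on ratio and attendance. The documents lean towards the single-group version but do not settle the matter.

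**What to change.** The sponsor should declare one design and align the synopsis, sections 1.1 to 1.4, Aim 2 section 2b, and Protection of Human Subjects sections 1a and 1b.

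**If single-group:**
- remove the RCT label in section 2b and the RCT, randomisation and two-arm wording in sections 1a and 1b;
- replace the 30-attender rule with enrolment of 40;
- delete the 12-month survey, or add it to sections 1.2, 1.3 and 1.4;
- tie the two-sample tests and relative risks to named groups, or delete them;
- report the result as an uncontrolled change from baseline.

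The cost is amendment wording and a consent check, with no extra patients.

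**If randomised:**
- rewrite the synopsis and sections 1.1 to 1.4 with the allocation ratio and total N;
- specify a baseline-adjusted between-arm comparison of everyone randomised;
- give one survey schedule, with payment for any 12-month survey.

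The cost is an amendment, a defined between-arm analysis, and possibly more than 40 patients, depending on the ratio and on whether the 30-attender rule is kept.

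Either way, check that the consent form, which was not available for this review, matches the declared design.
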